3. ANALYSIS SET

- Full Analysis Set

Full Analysis set consists of the subjects who are given at least one dose of the study drug.

4. CONSIDERATIONS for ANALYSIS

- Confidence coefficient
95% (two-sided)
- Level of significance
5% (two-sided)

- Display digit
[Mean, Confidence Intervals (CIs), Quartiles]
Round down to the one digit lower than significant digits of the data.
- [Standard Deviation]
Round down to the two digits lower than significant digits of the data.
- [Minimum and Maximum Values]
Display the data at the significant digits.
- [Proportion, Percentage]
Round to one decimal place.

5. OTHER DATA HANDLING

[Study Drug]

- Study drug exposure in days will be calculated as follows:
Date of last dose – date of first dose +1

[Actigraphy]

- Daily variation of sleep latency will be calculated at each assessment time point as follows:
Maximum value of sleep latency – minimum value of sleep latency

[Sleep Diary]

- Total nocturnal sleep time will be derived at each assessment time point as follows:
(Awaking hour – bedtime hour) – sleep latency
- Daily variation of sleep latency will be calculated at each assessment time point as follows:
Maximum value of sleep latency – minimum value of sleep latency

[HAM-D17]

- HAM-D17 total score (excluding sleep related score):
HAM-D17 total score – total score of sleep related score (question number 06, 07, 08)
- HAM-D17 total score (sleep related score only):
Total score of sleep related score (question number 06, 07, 08)

[Demographic Characteristics]

- Disease Duration (year)
Duration of insomnia or depression = (date of first dose – onset date of insomnia or depression + 1) / 365.25

For calculation, the onset date is regarded as the first of the month.

[3DSS]

3DSS Questionnaire Instructions

- Choose the best number which describes yourself over the past one month.
- The question is for your daily life, and you don't need to consider any special cases.
- Please fill in the number, or mark it.
- Pen, pencil, marker pen can be used.
- If you correct your answer, please erase it or mark "x" on your previous answer.

No.		Strongly Agree	Agree	Disagree	Strongly Disagree
1	I sleep for less than 6 hours on weekdays.	[1]	[2]	[3]	[4]
2	I cannot get enough sleep even though I want to.	[1]	[2]	[3]	[4]
3	I go to bed at a fixed, regular time on weekdays and weekends.	[1]	[2]	[3]	[4]
4	I wake up at a fixed, regular time on weekdays and weekends.	[1]	[2]	[3]	[4]
5	I have a well-balanced breakfast every day.	[1]	[2]	[3]	[4]
6	It takes me more than 30 minutes to fall asleep.	[1]	[2]	[3]	[4]
7	I wake up more than twice a night.	[1]	[2]	[3]	[4]
8	I wake up earlier than usual (for over 2 hours), and cannot fall asleep again.	[1]	[2]	[3]	[4]
9	I don't sleep soundly.	[1]	[2]	[3]	[4]
10	I worry that I cannot fall asleep.	[1]	[2]	[3]	[4]
11	I don't feel free from sleepiness or fatigue when I wake up.	[1]	[2]	[3]	[4]
12	I feel sleepy not only in the afternoon, but also in the morning and/or evening.	[1]	[2]	[3]	[4]
13	I often doze off.	[1]	[2]	[3]	[4]
14	"Morningness" is better suited to me than "Eveningness".	[1]	[2]	[3]	[4]

No.		Strongly Agree	Agree	Disagree	Strongly Disagree
15	What time do you wake up on weekdays? [1] --> 6 A.M. or earlier [2] --> Around 6:30 A.M. [3] --> Around 7 A.M. [4] --> Later than 7 A.M.	[1]	[2]	[3]	[4]

- Phase scale score

Phase scale score is the total score of the question number 3, 4, 5, 14 and 15, and each score is assigned according to the answers as below.

[1]=3, [2]=2, [3]=1, [4]=0

- Quality scale score

Quality scale score is the total score of the question number 6 to 10, and each score is assigned according to the answers as below.

[1]=0, [2]=1, [3]=2, [4]=3

- Quantity scale score

Quantity scale score is the total score of the question number 1, 2, 11, 12 and 13, and the score for each answer is assigned as below.

[1]=0, [2]=1, [3]=2, [4]=3

[TEAE]

- A TEAE is an adverse event for which the date of onset occurred after the first dose of study drug.

[Non-serious TEAE]

- Non-serious TEAE is an adverse event experienced by more than 5 % of subjects, excluding serious AE (defined in the section 10.1.3 in the protocol).

6. SUBJECTS, DEMOGRAPHIC and OTHER BASELINE CHARACTERISTICS

6.1. Subject Disposition

6.1.1. Study Information

Analysis set: All subjects who are obtained informed consent

Analysis Items: The earliest date of informed consent

The latest date of the last date of administration

Version of MedDRA

Version of SAS

Analysis Methods: For the above analysis items, the following analysis will be performed.

- (1) The above items will be listed.

6.1.2. Eligibility of Subjects

Analysis set: All subjects who are obtained informed consent

Analysis Items: Randomization into the treatment period of the study

[Yes, No (and the reason)]

Analysis Methods: For the above analysis items, the following analysis will be performed.

- (1) The number of subjects and the percentage will be calculated.

6.1.3. Subject Disposition

6.1.3.1. Status at the End of Study

Analysis set: All subjects who enter the treatment period

Analysis Items: Status at the end of study

[Complete, Incomplete (and the reason)]

Analysis Methods: For the above analysis items, the following analysis will be performed.

- (1) The number of subjects and the percentage will be calculated.

6.1.4. Protocol Deviations and Analysis Datasets

6.1.4.1. Protocol Deviations

6.1.4.1.1 Protocol Deviations on the treatment period

Analysis set: All subjects who enter the treatment period

Analysis Items: Protocol Deviations

[Major GCP violations, Deviations of protocol entry criteria, Deviations of discontinuation criteria, Deviations related to treatment procedure or dose, Deviations concerning excluded medication or therapy, Deviations to avoid emergency risk, Other deviations]

Analysis Methods: For the above analysis items, the following analysis will be performed.

The number of subjects with any protocol deviations will be calculated, and classified into the above categories. Subjects with two or more deviations will be counted for each deviation.

- (1) The number of subjects and the percentage will be calculated.

6.1.4.2. Datasets Analyzed

6.1.4.2.1 Datasets Analyzed

Analysis set: All subjects who enter the treatment period

Analysis Items: Protocol deviations [Inclusion, Exclusion]

Full Analysis Set

Analysis Methods: For the above analysis items, the following analysis will be performed.

- (1) The number of subjects and the percentage will be calculated. Subjects with two or more deviations will be counted for each deviation.
- (2) The number of subjects in Full Analysis Set and the percentage will be calculated based on the subjects who enter the treatment period.

6.2. Demographics and Other Baseline Characteristics

6.2.1. Distribution of Demographics

Analysis set: All subjects who are given at least one dose of the study drug

Analysis Items:

Age (years) [Min<= - <65, 65<= - <=Max]

Gender [Male, Female]

Height (baseline) (cm)

[Min<= - <150, 150<= - <160, 160<= - <170,

170<= - <=Max]

Weight (baseline) (kg)

[Min<= - <40.0, 40.0<= - <50.0,

50.0<= - <60.0, 60.0<= - <70.0, 70.0<= - <=Max]

BMI (baseline) (kg/m²)

[Min<= - <18.5, 18.5<= - <25.0, 25.0<= - <=Max]

Alcohol consumption per week

[0 day, 1-2 days, 3-5 days, 6-7 days]

Daily smoking status

[Non-smoking, Less than 20 cigarettes, 20 cigarettes
or more]

Insomnia

- Duration of disease (years)
- Initial episode/recurrence [Initial episode, Recurrence]
- Non-pharmacological therapy [Yes, No]

Depression

- Duration of disease (years)
- Initial episode/recurrence [Initial episode, Recurrence]
- Psychotherapy [Yes, No]

Sleep latency by actigraphy (baseline)

Sleep latency by sleep diary (baseline)

Total nocturnal sleep time by actigraphy (baseline)

Nocturnal wake time by actigraphy (baseline)

Number of nocturnal awakenings by actigraphy (baseline)

Sleep efficiency by actigraphy (baseline)

Total nocturnal sleep time by sleep diary (baseline)

Number of nocturnal awakenings by sleep diary (baseline)

Daytime activity level by actigraphy (steps) (baseline)

Analysis Methods: For the above analysis items, the following analysis will be performed.

- (1) The number of subjects and the percentage will be calculated for discrete variables, and summary statistics will be calculated for continuous variables.

6.2.2. Medical History and Concurrent Medical Conditions

Analysis set: All subjects who are given at least one dose of the study drug

Analysis Items: Medical history, Concurrent medical conditions

Analysis Methods: History events and concurrent medical conditions will be coded using the MedDRA dictionary and tabulated by System Organ Class (SOC) and Preferred Term (PT). SOCs will be sorted in alphabetical order, and PTs will be sorted in decreasing frequency order.

- (1) The number of subjects and the percentage will be calculated for medical history by SOC/PT.
- (2) The number of subjects and the percentage will be calculated for medical conditions by SOC/PT.

Subjects with one or more events within a level of MedDRA term is counted only once in that level.

6.2.3. Medication History and Concomitant Medications

Analysis set: All subjects who are given at least one dose of the study drug

Analysis Items: Medication history

Previous use of hypnotics

[Yes (previous use of Benzodiazepine hypnotics, previous use of Non-benzodiazepine hypnotics, previous use of other hypnotics), No]

Concomitant Medications

Analysis Methods: The number of subjects and the percentage will be calculated for the above analysis items. Medications will be coded using the WHO (World Health Organization) Drug. Coded medications will be sorted in decreasing frequency order. Medications used more than once within a subject will be counted only once for the coded medication.

6.3. Study Drug Compliance and Exposure

6.3.1. Study Drug Compliance

Analysis set: All subjects who are given at least one dose of the study drug.

Analysis Items:

Study drug compliance [Properly (90% or more), Generally (70% or more), Half (50% or more), Less than half (less than 50%)]

Antidepressants Compliance [Properly (90% or more), Generally (70% or more), Half (50% or more), Less than half (less than 50%)]

Change of antidepressants dosage regimen [Yes, no]

Time point: Week 4, Week 8

Analysis Methods: For the above analysis items, the following analysis will be performed.

- (1) The number of subjects and the percentage will be calculated for each category.

6.3.2. Study Drug Exposure

Analysis set: All subjects who are given at least one dose of the study drug.

Analysis Items:

Duration of study drug exposure (days) [$1 \leq - < 29$, $29 \leq - < 58$, $58 \leq - \leq \text{Max}$]

Analysis Methods: For the above analysis items, the following analysis will be performed.

- (1) The number of subjects and the percentage will be calculated for discrete variables, and summary statistics will be calculated for continuous variables.

7. EFFICACY EVALUATIONS

7.1. Primary Endpoint and the Analytical Methods

7.1.1. Change from Baseline in Sleep Latency by Actigraphy

Analysis set: Full Analysis Set

Analysis items: Sleep latency by actigraphy

Time point: Baseline, Week 4, Week 8, End of the treatment period

Analysis methods: For the above analysis items, the following analysis will be performed.

- (1) As the analyses for primary endpoint, summary statistics and two-sided 95% confidence interval (CI) of the mean will be calculated for both change and percentage change from baseline to the end of treatment period, and one sample t-test will be conducted to assess the change within a subject. The same analyses as described above will be performed for change and percentage change at Week 4 and Week 8. In addition, mean plots with +/- SD for change and percentage change will be displayed at each time point.
- (2) For change and percentage change from baseline to each time point, case plots will be illustrated at each time point.
- (3) For observed value at each time point, case plots will be displayed, and summary statistics and two-sided 95% CI of the mean will be calculated. Mean plots with +/- SD will be also displayed at each time point.

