5.2 Endpoints

5.2.1 Primary endpoint

Change in actigraphy-measured sleep latency* from baseline (i.e., start of the study treatment period) to the end of the treatment period

*: Mean value from the past 7 days

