6.2 Rationale for the Study Design

<Rationale for the study population>

For ramelteon, a drug approved for "improvement of sleep onset difficulty in insomnia", data have been limited on its efficacy and safety in insomnia patients with psychiatric disease, and construction of the clinical evidence is desired. Among psychiatric diseases, depression is common and often coexists with insomnia symptoms. Thus, the study population is set to insomnia patients with depression.

<Rationale for the study design>

An uncontrolled, open-label design is employed in light of feasibility of this post-marketing clinical research, although the primary objective is to explore the effect of ramelteon in treating insomnia patients with a history of co-morbid depression.

<Rationale for the dosage>

The approved dosage and method of administration for ramelteon are employed.

<Rationale for the endpoints>

The "Guideline for Clinical Evaluation of Hypnotic Agents" (Notification No. 1213-1 of the Evaluation and Licensing Division, Pharmaceutical and Food Safety Bureau, dated December 13, 2011) recommends the use of polysomnography for objective efficacy evaluation in addition to the use of patient-recorded sleep logs for subjective efficacy evaluation. While polysomnography is a complex examination and repeated polysomnography can impose heavy burden on participants, actigraphy has been recognized to provide sleep data highly correlated with those provided by polysomnography and is a simple tool posing less burden to participants. Thus, actigraphy is selected as an objective assessment tool in this study¹⁰⁾. For subjective measures, this study uses a sleep diary, as well as the Patient Global Impression (PGI) as an index of global improvement, and the 3 Dimensional Sleep Scale (3DSS) as a new tool to assess sleep dimensions including sleep phases. The HAM-D17 is selected for evaluation of depressive symptoms, in line with preceding studies.

The safety will be evaluated based on adverse events, body weight.

<Rationale for the treatment duration>

The treatment duration is set to 8 weeks on the basis of the Japanese long-term clinical trial of ramelteon (24-week treatment), which demonstrated gradual

manifestation of the efficacy of ramelteon on sleep latency under repeated dosing over a certain period, and the efficacy peaked around Week 8.

<Rationale for the sample size>

See Section 13.3

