13.1.5 Significance level and confidence coefficient

Significance level: 5% (two-sided testing)

Confidence coefficient: 95% (two-sided estimation)

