13.3 Determination of Sample Size

The sample size is set to 30 in light of feasibility of this study to investigate the effect of ramelteon in insomnia patients with depression. This planned sample size is not based on statistical power calculation.

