7.2. Secondary Endpoints and the Analytical Methods

7.2.1. Secondary Endpoints and the Analytical Methods

Analysis set: Full Analysis Set

Analysis items:

Sleep latency by actigraphy

Total nocturnal sleep time by actigraphy

Nocturnal wake time by actigraphy

Number of nocturnal awakenings by actigraphy

Sleep efficiency by actigraphy

Total nocturnal sleep time by sleep diary

Number of nocturnal awakenings by sleep diary

Daytime activity level by actigraphy (steps)

Time Point: Baseline, Week 4, Week 8, End of the treatment period

Analysis Methods: For the above analysis items, the same analyses as described in 7.1.1. will be performed for secondary endpoints.

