10.6. Examination of Subgroups

The subgroup analyses will be performed to examine the primary endpoints using the same analysis methods as 7.1.1(1). The analyses will be performed for the data at the end of treatment period only.

Subgroups:

- Medication history
[Previous use of Benzodiazepine hypnotics,
No previous use of Benzodiazepine hypnotics (Previous use of Non-benzodiazepine hypnotics),
No previous use of Benzodiazepine hypnotics (No previous use of Non-benzodiazepine hypnotics and previous use of other hypnotics),
No previous use of hypnotics]
- Concomitant use of Benzodiazepine anxiolytics [Yes, No]
- Concomitant use of SSRI or SNRI [Yes, No]
- Duration of insomnia [< 3years, 3years<=]
- Duration of depression [< 3years, 3years<=]
- Phase scale score in 3DSS at Baseline [< 9, 9<=]

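### Zero is not the no-effect value for the mean percentage change that SAP 7.1.1(1) tests; for sleep latency the direction of the bias is unknown, so the measure should be descriptive

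*SAP*

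**What the plan says.** Protocol 5.2.1 defines the primary endpoint as "Change in actigraphy-measured sleep latency* from baseline (i.e., start of the study treatment period) to the end of the treatment period", using 7-day means. Protocol 13.1.3 applies a one-sample t-test to that absolute change, at the two-sided 5% level of 13.1.5.

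SAP 7.1.1(1), under the primary-endpoint analyses, says that summary statistics and a CI "will be calculated for both change and percentage change from baseline to the end of treatment period, and one sample t-test will be conducted". It repeats this for both measures at Weeks 4 and 8. No null value is written; zero is implied. The revision history (SAP 11) shows that percentage change entered with version 2.0.

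The test then spreads. SAP 7.2.1 says "the same analyses as described in 7.1.1. will be performed for secondary endpoints". SAP 7.3.2(3) and 7.3.3(3) use the same wording for the HAM-D17 totals and the 3DSS scores. SAP 10.6 applies 7.1.1(1) within each subgroup level. SAP 10.5 makes no multiplicity adjustment.

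Two other provisions matter. Inclusion criterion 9 (Protocol 7.1) requires run-in actigraphy with latency of at least 30 minutes and sleep time of at most 6.5 hours on at least 3 days. The baseline is that same week: Week -1 to 0 in Protocol 9.3.1, Day -7 to Day 1 in SAP 2.

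**The concern.** Percentage change is asymmetric: a halving counts -50 and a doubling +100. Two patients who go from 60 to 40 minutes and from 30 to 45 minutes have a mean absolute change of (-20 + 15)/2 = -2.5 minutes, but a mean percentage change of (-33.3 + 50)/2 = +8.3%. If nothing but noise separates baseline from end of treatment, the average ratio still exceeds 1, and a t-test against zero treats that excess as signal.

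The SAP puts this test beside the protocol's measure without ranking the two. If they disagree, in significance or in sign, the report has two answers under one primary endpoint and no rule for choosing between them.

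**Working it through.** **Inputs.** From the documents: n = 30, one arm, two-sided 5%, one-sample t-test, criterion 9, and a baseline taken from the run-in week. The size is a feasibility figure (Protocol 13.3: "This planned sample size is not based on statistical power calculation"), and no SD, correlation or expected effect is given. There is therefore no figure of the plan's to reproduce, and every SD and median below is an assumption shown as a range.

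**Step 1: asymmetry alone, no selection.** For a log-normal ratio end/baseline with geometric mean ratio G and log-ratio SD tau, the expected percentage change is G·exp(tau²/2) − 1. With no effect, G = 1:

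- tau 0.1: exp(0.005) − 1 = +0.5%
- tau 0.2: exp(0.020) − 1 = +2.0%
- tau 0.3: exp(0.045) − 1 = +4.6%
- tau 0.5: exp(0.125) − 1 = +13.3%
- tau 0.7: exp(0.245) − 1 = +27.8%

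Simulated trials of n = 30 (nominal 2.5% in each tail):

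| tau | False increase | False decrease | Power for a 20% shorter latency: percentage test | Same: log-ratio test |
|---|---|---|---|---|
| 0.2 | 5.8% | 1.1% | 100% | 100% |
| 0.3 | 8.6% | 0.6% | 88% | 98% |
| 0.5 | 15.7% | 0.3% | 25% | 65% |
| 0.7 | 24.0% | 0.1% | 6% | 40% |

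**Step 2: add the latency part of criterion 9, no drug effect.** Nightly log-normal latencies, 7-night means, entry only if at least 3 of 7 baseline nights reach 30 minutes. Assumed log SDs: 0.4–0.6 between patients, 0.2–0.4 patient-by-period, 0.6–0.9 night to night. Ranges run over five combinations of these.

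| Median latency before selection | Expected % change | Expected absolute change (min) | % test: false worsening | % test: false improvement | Log-ratio test: false improvement |
|---|---|---|---|---|---|
| 20 min | -12.5 to -1.3 | down to -11.0 | 0–0.5% | 8–37% | 39–79% |
| 30 min | -1.4 to +6.4 | -7.6 to -3.2 | 0.5–2.9% | 2.3–7.4% | 18–36% |
| 45 min | +5.6 to +14.9 | -4.6 to -1.3 | 4.9–7.8% | 0.6–1.3% | 7–12% |
| 60 min | +8.3 to +22.0 | -2.8 to -0.6 | 8.7–14.3% | 0.4–0.6% | 4–6% |

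A normal model (mean 45, SD 15, correlation 0.3–0.7) gives +3.9% to +9.1% without selection and -2.4% to -1.0% once baselines under 30 minutes are cut off.

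**Step 3: separate the two forces.** One mid-range setting (log SDs 0.5, 0.3 and 0.75), medians 20, 30, 45 and 60:

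- arithmetic mean percentage change: -7.4, +2.4, +10.5, +14.8
- geometric mean percentage change: -21.4, -13.5, -7.2, -4.0
- difference, which is the asymmetry: 14.0, 15.9, 17.7, 18.8 points

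Selection therefore offsets the asymmetry but does not remove it. In this setting, at medians 30, 45 and 60 the expected absolute change is -4.9, -2.9 and -1.6 minutes while the expected percentage change is positive. The two sample means differ in sign in 32–42% of trials (16% at median 20).

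**Step 4: other endpoints.** For total sleep time, an assumed tau of 0.10–0.15 gives +0.5% to +1.1%, which is negligible. For step counts, tau 0.4 gives exp(0.08) − 1 = +8.3%.

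**The case against.** The strongest objection is that Step 1 describes a trial other than this one. Patients are admitted because their latency was long in the baseline week, so baseline and end values are not exchangeable and regression to the mean lowers the no-effect change. That stands. A reader might infer from the asymmetry that the percentage test always works against the drug and mainly produces false worsening. The documents do not support this: at a median of 20 minutes the commoner false signal is improvement. For the same reason the power figures in Step 1 do not carry over to this sample.

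A second objection is that a t-test of mean percentage change does test mean percentage change, and that zero is not the no-drug-effect value for absolute change either: Step 2 puts that at -0.6 to -11 minutes. Also correct. Protocol 6.2 says "An uncontrolled, open-label design is employed in light of feasibility", and regression to the mean affects every within-group test here. The ratio asymmetry, however, is an additional distortion that absolute change does not have.

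Third, the t-test clause might be read as covering absolute change only. The next sentence of 7.1.1(1) repeats the same analyses for both measures at Weeks 4 and 8, which favours the reading that both are tested, though the wording could be clearer.

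Finally, the study is exploratory and has no decision rule on percentage change. That limits the severity.

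**Conclusion.** The point holds in a limited form. Zero is not the no-effect value of the mean percentage change. The asymmetry pushes it up, by an amount that depends on tau: negligible at 0.1, about 13% at 0.5. Criterion 9 pushes it down. For sleep latency the net no-effect value lay between about -12% and +22% over the assumptions tried, so its sign is unknown, and it can contradict the absolute change. Two opposing biases of unknown size do not amount to a correction.

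It would be wrong to conclude that the primary analysis is invalid. The protocol's endpoint and test use absolute change, which lacks the asymmetry; the affected analysis is the SAP version 2.0 addition. It would also be wrong to call every endpoint materially biased, as the total sleep time figures show. This is a should-fix, not a must-fix.

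The sizes rest on assumed log-normal or normal models and assumed SDs. The sleep-time part of criterion 9 and the HAM-D17 sleep-item criterion were not simulated; they would probably push the change further down.

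**What to change.** Keep absolute change as the only tested primary and secondary measure. In SAP 7.1.1(1), 7.2.1, 7.3.2, 7.3.3 and 10.6, drop the one-sample t-test of percentage change and label that measure descriptive. A t-based 95% CI excludes zero exactly when the test rejects, so if the CI stays, add a note that zero is not its no-effect reference.

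If a relative measure is wanted for strictly positive variables (sleep latency, sleep time, steps), report the mean of ln(end/baseline), back-transformed to a geometric-mean percentage change with a 95% CI. Do not use it for variables that can be zero or for bounded scores: awakenings, sleep efficiency, HAM-D17, 3DSS.

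Add one sentence to the SAP saying that no within-group test in this uncontrolled study isolates a drug effect.

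The cost is SAP wording and a few lines of code. There are two downsides. A weekly mean of exactly 0 would need a stated rule on the log scale. More importantly, the log ratio removes the asymmetry but not the regression to the mean from criterion 9, and it can show more false improvement than percentage change does (39–79% against 8–37% at a median of 20 minutes). That is why it is proposed as an estimate with a CI and not as a replacement test, and its CI needs the same caution.
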